KB will refine and complete the digital programming of PN in consultation with the research team. Investigators have developed goals and specific instructional/behavioral objectives and content for the PN in Phase I. During Phase II, KB will iteratively share content with all members of the team who will review and provide feedback for any remaining revisions. We used a combination of emails, telecommunications, Zoom teleconferencing, and in-person meetings in Phase I (meeting weekly and more often as needed). We will utilize this same approach in Phase II. This process will continue until all necessary improvements are made. Following completion of the digital programming for the remaining modules, we will conduct a usability study that mirrors the approach we used in Phase 1. The functionality of the PN program will be tested by KB on a small group of parents (~n = 5-7). Edits will be made based on these findings and then tested again on another small group of parents (~n = 5-7). Based on our experience on the development time in Phase I, we anticipate this process to be completed in 6 months.

**Limitations and Alternative Methods for Objective 1.** Face-to-face delivery and/or a longer curriculum may be more effective in reducing substance use. Future research should compare modalities, but the current design facilitates delivery with minimal training and increased consistency, maximizing usability with varied groups. A native mobile app could be produced but it is more expensive and can take longer to produce for multiple device operating systems, is more challenging to update, and its use cannot be as easily monitored as a web app.

**Milestones/Deliverables for Objective 1.** The benchmark for Objective 1 is when all of the above steps are accomplished and PN is revised to specifications and fully operational with a high degree of usability as expressed in SUS scores above the 68 standard.

**Objective 2: Conduct a randomized clinical trial to evaluate outcomes of the PN curriculum. Randomized Trial Design.** The design is a two-arm RCT (PN vs. active control) with 3 waves of data collection: pre-intervention baseline, short-term follow-up (1-month), and longer-term follow-up (6-month). The study will enroll a nationally representative sample of 400 parent-student dyads through GfK Custom Research (formerly known as Knowledge Networks). Youth will complete assessments of all the variables in

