As noted above, teens who complete their consent will be routed to an online survey. After the baseline assessment, parents will be randomized equally to 1 of 2 groups. Parents in the treatment condition will receive a link to KB’s secure server to access PN and complete a brief question set assessing their parent communication style. Parents in the control condition will receive a link to that server to access publicly available SAMHSA alcohol prevention materials for parents. Both conditions take the same length of time to navigate. Parents in both conditions will be instructed to access the materials and discuss the information with their teens during the next month. Thus, the proposed research will have a strong active control condition for which to examine differences in effects increasing the rigor of the study. The link to the website will contain instructions on how to register and use the site. Parents who do not register with the website will receive reminders every 5 days for three weeks; after three weeks, study staff will contact parents by telephone and encourage them to register. RP staff will provide technical assistance if parents have problems using the website. In our previous studies, we have had parental compliance rates with web surveys, parenting materials

from the Parent Handbook, parent-ratings of the Parent Handbook and so on, that have reliably exceeded 88%. We anticipate no problems regarding use of the PN in the proposed research.

Teen participants in both the treatment and control groups will receive a follow-up survey (~15 minutes to complete) at 1 and 6 months post-baseline, which will allow us to examine any changes in the proposed mediator variables. Parents randomized to the PN condition will complete a brief question set at the beginning of the PN intervention that assesses parenting communication style and allows for personalization. Parents also receive an immediate posttest to measure fidelity and reactions to PN. Baseline, 1- and 6-month follow-up surveys will each take approximately 25-30 minutes to complete.

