**Participant retention and plans to increase retention.** Our retention goals are to have a final sample representative of the U.S. population, free of sample bias, and of sufficient power to address our study aims (see Attrition and Statistical Power sections below). This has been our experience in two large-scale national sample studies with GfK. As indicated, GfK's panels tend to outperform other large national panels on known and standard benchmarks (e.g., Census data). GfK's panels typically observe a 2% monthly panel attrition rate that is not-study specific, study-specific retention rates of 80% for short-term follow-ups (1-3 months) and 70% retention in longer-term follow-ups (6-12 months). In [name]'s recent national RCT study with GfK, he observed a 78% participation rate for teens similar to the proposed study and retained 88% at 12 months. Our procedures make every attempt to reduce attrition by keeping respondent contact information current and using methods we have employed in our past work. First, in the initial baseline survey, participants will list and provide contact information for two individuals they DO NOT live with whom we may contact in the event we are unable to locate participants with our contact information, as well as a cell phone number at which they can receive text message reminders. Second, at the beginning of each post-assessment, participants will be contacted by email and asked to update their own contact information and that of the two individuals they indicated as contact individuals in the previous assessment. If they do not respond, we will follow-up by phone. Finally, we will provide sufficient incentives and multiple contacts (up to 7 email reminders) that help with high retention. Using these procedures for the 400 parent-student dyads at baseline, we anticipate the 2% monthly non-study specific attrition will result in n's of 320 and 280 dyads at the 1- and 6-month follow-ups.

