**Attrition analyses.** We will first examine if the attrition is random by forming a dummy variable that indicates completion or drop-out at each assessment. The dummy variable will be correlated with key variables in the study (e.g., Group, drinking outcomes). In the past, we have observed nonsignificant correlations suggesting that the attrition has been random and then used the most advanced multiple imputation techniques to impute missing data. We then analyze all cases with the imputed data. Although we have not observed differential attrition by condition, we recognize the potential. We will reduce this possibility by providing the controls with an online link to the intervention at the completion of the 6-month assessment. Thus, all conditions will be identical except for the timing of intervention. However, if we should observe non-trivial correlations (e.g.,  $> .2$ ) between the dummy variable reflecting completers vs. drop-outs, we will include the dummy coded variable as a covariate in subsequent analyses and attempt to interpret significant effects.

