### **Data Analysis**

We first discuss general issues and then turn to analyses specific to the aims of the proposed research.

**Missing Data.** In general, missing data is infrequent and not problematic, but occasions may arise where this must be formally addressed. Data can be missing at random (MAR), missing completely at random (MCAR) or missing in a systematic way. To gain perspective on the nature of the missingness for a given variable, we will create a dummy variable coded for each respondent: 1 = missing value on the variable or 0 = not missing. We will test for associations between this variable and others in the models. We also will apply Little's multivariate test for MCAR. Missing data also can result from attrition. We will differentiate these two sources of missingness and explore for each. We will use Full Information Maximum Likelihood (FIML) and multiple imputation (MI) or systematically model missing data bias, depending on the data and the models.

**Assumption Violations.** We will use bootstrapping to derive asymmetrical confidence intervals or robust methods to address assumption violations. Mplus offers algorithms for both. In general, we will be sensitive to assumption violations and explore data cautiously.

**Outliers.** We will apply standard methods for outlier detection (e.g., analysis of leverage statistics, residuals, and dfBetas) and also use graphical approaches.

**Multiple Items, Variables, and Contrasts.** For all of our multi-item measures, we will evaluate the coefficient alphas and factor structures to ensure they are consistent with their psychometric histories. We will examine the intercorrelations and the results of exploratory or confirmatory factor analyses to guide choices about combining indices or latent constructs. When we conduct multiple significance tests, we will compare the robustness of our conclusions both with and without statistical corrections for multiple tests using the strategy discussed in Jaccard & Guilamo-Ramos. In general, we will use a Holm adjusted modified Bonferroni method or the False Discovery Rate (FDR) method for controlling experiment-wise error, both of which are more powerful than Bonferroni methods.

**Specification Error.** We will be sensitive to issues of specification error, being careful to explore a wide range of model diagnostics to protect against gross model misspecification.

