### **Specific issues and approaches for the analyses of the Specific Aims.**

**Aim 1: Evaluate the efficacy of PN intervention.** The primary focus of the analyses will document differences on our primary outcomes (alcohol use and alcohol-related harms) and secondary outcomes (marijuana use, nicotine use, and their combined use with alcohol) between the groups (PN/Control) using a mixed measures analysis of variance. A 2 X 3 (groups X time) MANCOVA will test the impact of the PN intervention on our outcome variables contrasting baseline tendencies against follow-up assessments (3 waves: baseline, 1 mo., and 6 mo.). For Aim 1 (analysis of efficacy), we will conduct an intent-to-treat analysis that will include all individuals who have been randomized to a condition. We will also examine differences in all outcomes by sex of the student (as a relevant biological variable), sexual orientation, and gender identity adding these as covariates to the analyses. We will be sensitive to inflated experiment-wise error rates and control these with modified Bonferroni methods.

**Aim 2: Examine mediators.** The second aim examines mediation paths in Figure 1 using SEM. We will follow the recommendations of MacKinnon (joint significance). For example, we will examine the relationship between the effects of the PN on predictors at the immediate post-PN assessment (1 mo. follow-up) and their subsequent effects on outcomes at the 6 month follow-up. The models will be statistically over-identified. We will examine global fit indices and focused indices of fit diagnostic of specific points of ill fit in the model (e.g., standardized residuals for predicted minus observed variances and covariances, and modification indices). We will use robust standard errors and bootstrapping. In the face of poor model fit, we will examine diagnostics that are conceptually meaningful and will significantly improve model fit.

[figure not shown]

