### Retention Plan

Our retention goals are to have a final sample representative of the U.S. population, free of sample bias, and of sufficient power to address our study aims (see *Attrition and Statistical Power* section). This has been our experience in [name]'s large-scale national sample studies with GfK.see 57,60 As indicated, GfK's panels tend to outperform other large national panels on known and standard benchmarks (e.g., Census data), both overall and in many individual categories. GfK's panels typically observe retention rates of 80% for short-term follow-ups (1-3 months) and 70% retention in longer-term follow-ups (6-12 months).

Our retention plans include incentives, reminder messages (texts, emails), multiple phone numbers, and contact information for close family and friends. First, teens will each be offered a minimum of \$45 for completion of all assessments. Parents will receive a minimum of \$25 for participating in the intervention and completing one assessment. To increase participation and retention at later waves, students and parents will be offered small bonuses of \$5 for assessments 1 and 2 (youth) and intervention and assessment (parent) completed within five days. Second, in the initial baseline survey, participants will list and provide contact information for two individuals they DO NOT live with whom we may contact in the event we are unable to locate participants with our contact information, as well as a cell phone number at which they can receive text message reminders. Third, at the beginning of each post-assessment, participants will be contacted by email and asked to update their own contact information and that of the two individuals they indicated as contact individuals in the previous assessment. If they

do not respond, we will follow-up by phone. Finally, we will use multiple contacts (up to 7 email or text reminders) that help with high retention. Using these procedures for the 400 parent-student dyads at baseline, we anticipate retaining minimally 80% of the participants across the 12-month follow-up (n = 320 dyads).

Phase II, Year 1 Timeline												
Month	1	2	3	4	5	6	7	8	9	10	11	12
Finalize PN	x	x	x	x	x	x						
Recruitment (GfK)							x					
Training	x	x						x				
Pretest						x						
Treatment/Active Control									x			
Posttest #1										x		
Data Cleaning											x	x
Report Writing											x	x

Phase II, Year 2 Timeline												
Month	13	14	15	16	17	18	19	20	21	22	23	24

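### Adding a drop-out dummy as a covariate does not correct non-random attrition, can move the Aim 1 arm effect, and has no stated order against FIML or multiple imputation

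*Combined protocol and SAP*

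**What the plan says.** The Attrition analyses paragraph forms a completer/drop-out indicator at each assessment and correlates it with arm, drinking outcomes and other key variables. On the risk by arm it says: "Although we have not observed differential attrition by condition, we recognize the potential". If correlations are non-trivial (the example is above .2), the action is: "we will include the dummy coded variable as a covariate in subsequent analyses and attempt to interpret significant effects". Multiple imputation appears in that paragraph as what the team did in the past when attrition looked random.

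The Missing Data paragraph under Data Analysis also covers attrition. It lists FIML and multiple imputation, and continues: "or systematically model missing data bias, depending on the data and the models". It does not say which method governs once the attrition trigger has fired.

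For Aim 1 the plan promises: "we will conduct an intent-to-treat analysis that will include all individuals who have been randomized to a condition". The model is a group by time MANCOVA over three waves. Neither section says whether the dummy enters as a main effect, with a time interaction, or in a model of change.

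On the amount of loss, the participant retention paragraph expects that attrition "will result in n's of 320 and 280 dyads at the 1- and 6-month follow-ups". The Retention Plan says: "we anticipate retaining minimally 80% of the participants across the 12-month follow-up (n = 320 dyads").

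**The concern.** A drop-out indicator is measured after randomization. If teens leave at different rates by arm, and leaving is also linked to drinking, the arms are no longer comparable within the completer and drop-out strata. Adjusting for the indicator compares arms within those strata, so it can create an arm difference where none exists or distort a real one. It also does not supply the missing outcomes.

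Differential attrition is the risk the plan itself names, and it is where the rule can do harm. The plan expects to lose 20% to 30% of dyads, so the rule may well come into play. The Aim 1 estimate could then depend on a covariate choice made after looking at the attrition data. The plan does not say that the dummy replaces imputation, and that is not claimed here. The problem is a stated rule that can disturb an otherwise sound imputed or likelihood estimate, with nothing to say which takes precedence.

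**Working it through.** **1. The plan's retention figures.** 400 x 0.80 = 320 and 400 x 0.70 = 280, so the retention paragraph's counts follow from its 80% and 70% study-specific rates. They do not follow from the 2% monthly attrition the same sentence credits: 400 x 0.98 = 392 and 400 x 0.98^6 = 354. The Retention Plan's 320 is 80%, over a 12-month follow-up that the three-wave design does not have. Both 70% and 80% are carried below.

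**2. When the trigger fires through arm.** With 1:1 allocation and overall retention p, r = 0.5 x gap / sqrt(p(1-p)). Setting r = .2 gives gap = 0.4 x sqrt(p(1-p)).
- p = 0.70: 0.4 x sqrt(0.21) = 0.183, about 18 points.
- p = 0.80: 0.4 x sqrt(0.16) = 0.160, 16 points.

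The trigger can also fire through drinking.

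**3. Teens observed at the wave.** In a model with intercept, arm, baseline and that wave's dummy, the dummy equals a constant. The design matrix has rank 3 of 4, in every simulated trial. The rule changes nothing here.

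**4. All randomized teens, imputed.** From the plan: N = 400, 200 per arm. Assumed: true effect 0, SD 1, baseline to follow-up correlation 0.6, two-sided 5% tests. Drop-out logit = a0 + 0.9(Z - 0.5) + slope term, where Z = 1 for PN; a0 = -1.0 (about 70% retained) or -1.65 (about 80%). Imputation by arm from baseline, 10 imputations, Rubin's rules, 1,500-2,000 trials per setting.
- Setting A: slope 0.9 x baseline drinking in PN only. Retention 61.5% (PN) and 80.9% (control); r(drop, arm) = 0.215.
- Setting B: slope 0.9 x baseline drinking in both arms. Retention 61.5% and 77.8%; r(drop, arm) = 0.18, r(drop, baseline) = 0.35.

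Imputation alone is unbiased. Shift in the arm effect from adding the dummy, in SD (negative favours PN):

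| Setting | Follow-up only | Change from baseline | Baseline as covariate |
|---|---|---|---|
| A, about 70% | -0.055 | +0.037 | 0.000 |
| B, about 70% | -0.076 | +0.051 | 0.000 |
| A, 81% | -0.049 | +0.032 | 0.000 |
| B, 80% | -0.060 | +0.040 | 0.000 |

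False-positive rates at about 70%, without then with the dummy:

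| Setting | Follow-up only | Change from baseline | Baseline as covariate |
|---|---|---|---|
| A | 4.6%, 7.3% | 4.3%, 5.7% | 4.0%, 4.0% |
| B (two runs) | 4.8-5.1%, 9.4-11.3% | 5.1-5.4%, 7.4-7.5% | 5.2-5.5%, 5.3% |

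Drop-out related to baseline drinking only, or to arm only, gives a shift of 0.000 in all three models.

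**5. The rule as written, with the dummy added only when a correlation exceeds .2.** At N = 400 and about 70% retention it fired in 81% of trials (A) and 99.9% (B). False-positive rates were 7.2% and 10.9% (follow-up only) and 6.4% and 7.3% (change), against about 5% without the rule.

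**6. Group by time model, dummy as main effect only.** On one complete three-wave data set the 6-month coefficient was -0.13249 with and without it: a time-constant main effect cannot touch a within-person contrast. In a likelihood fit to observed rows (known covariance, 4,000 trials) the shift was +0.018 (A) and +0.026 (B) at about 70% retention, and +0.016 and +0.020 at about 80%. False positives were 4.7-5.7%.

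**7. A separate simulation with stronger drop-out.** Three waves, correlation 0.6, 30% loss, log-odds +1.1 for one arm and +1.0 per SD of drinking; imputation from arm, baseline and 1-month values.
- Drop-out on arm and baseline: 6-month mean shifted -0.10, false positives 4.8% to 15.3%; change shifted +0.06, 5.6% to 8.4%.
- Drop-out on arm and 1-month drinking: 6-month mean shifted -0.10, 5.2% to 13.8%; change did not shift. The baseline-adjusted 6-month effect moved from 0.00 to -0.04, so a baseline covariate is not always protective. The fully observed 1-month effect, adjusted for baseline, moved from 0.00 to -0.11 when the 6-month dummy was added.

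**8. Drop-out on the unseen 6-month value.** This bias is not caused by the rule. In the set-up of step 4, with the slope on the 6-month outcome in PN:

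| Retained | Model | Imputation alone | With dummy |
|---|---|---|---|
| 71% | Follow-up only | -0.202 | -0.232 |
| 71% | Change | -0.197 | -0.173 |
| 71% | Baseline covariate | -0.199 | -0.198 |
| 81% | Follow-up only | -0.137 | -0.164 |
| 81% | Change | -0.136 | -0.114 |
| 81% | Baseline covariate | -0.136 | -0.135 |

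The dummy worsens the bias in one model, trims it in another and leaves it in the third.

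**The case against.** The largest shifts come from a follow-up-only comparison, while the plan specifies group by time. In that model a main-effect dummy shifts the effect by nothing on imputed data and by 0.02 to 0.03 SD under likelihood, with near-nominal error. This stands, but the plan does not fix the form. If the dummy interacts with time, the change-from-baseline figures are the nearest guide. Where the dummy is harmless, it also corrects nothing.

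The trigger might rarely fire. Step 5 answers this for the assumed settings. Elsewhere it may be rare: through arm alone it needs a gap of 16 to 18 points, and the plan reports no differential attrition in past studies.

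Only a wave's own dummy is constant among teens seen at that wave. This is correct. The 6-month dummy does vary among teens seen at 1 month, but there it can bias a fully observed comparison (step 7).

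Simulation error on rejection rates is about 0.005 to 0.006, so the 5.7% for change in setting A cannot be told apart from 5%. This stands.

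FIML and multiple imputation are already listed for attrition. This also stands, and it makes the fix cheap, but no order of precedence is given.

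The bias from outcome-dependent drop-out is not the rule's doing, and using 1-month outcomes in the imputation reduces the -0.20 to about -0.175 to -0.19. Both are accepted. That bias supports a sensitivity analysis and does not count against the rule.

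**Conclusion.** The concern holds. The dummy rule is not a valid correction for attrition bias. When drop-out relates to both arm and drinking, it can shift the Aim 1 arm effect by about 0.03 to 0.08 SD in the main settings and up to about 0.11 SD under stronger drop-out, with opposite signs in different models. The mean shift is zero in these cases:
- drop-out is unrelated to arm;
- drop-out relates to arm only;
- baseline is a covariate and drop-out depends only on arm and baseline;
- the dummy is a main effect only in a group by time model on imputed data.

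The sizes depend on an assumed correlation of 0.6 and assumed drop-out models, since the documents give neither. That the rule conditions on a post-randomization variable, and that no order against FIML or imputation is stated, does not depend on those assumptions. The effect is modest and avoidable, so this should be fixed before analysis.

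**What to change.** - Delete the dummy-covariate rule and its trigger from the Attrition analyses paragraph.
- State that Aim 1 uses FIML or multiple imputation for all randomized dyads, with arm, baseline substance use and 1-month outcomes as predictors, whatever the attrition tests show.
- Report retention by arm and the attrition correlations as description only.
- Add one delta-adjusted or pattern-mixture sensitivity analysis for drop-out that depends on unseen drinking. The attrition correlations cannot test for this, because the 6-month outcome is missing for those who left.
- Reconcile the 6-month retention figure (280 in the participant retention paragraph, at least 320 in the Retention Plan), the 2% monthly explanation and the reference to a 12-month follow-up.

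The cost is plan wording and a little more analysis. Imputation and Mplus are already planned, and no new data are needed.
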